Official Title:

Determining the Impact of Combined Hormonal Contraceptives on Ulipristal Acetate

Principal Investigator:

[name], MPH

Professor, Department of Obstetrics and Gynecology
Oregon Health & Science University

NCT No:

NCT02577601

Protocol Version Date:

February 13, 2017

Determining the impact of combined hormonal contraceptives on ulipristal acetate

PI: [name] [name], Dept. OB/GYN

Funding: Investigator initiated, Society of Family Planning

Specific Aim:

1. To define whether starting COCs in close succession (2days) following the administration of the anti-progestin, ulipristal acetate, interferes with its efficacy as an EC.
2. To determine if differences exist between obese and normal BMI women in the pharmacokinetics of ulipristal acetate-based EC (pilot data)

Background

The availability of highly effective options for emergency contraception (EC) is critical for women wanting to avoid pregnancy following an act of unprotected intercourse. An anti-progestin, ulipristal acetate (UPA; ella™), has emerged as one of the most effective oral options¹. *In vitro* studies have shown that UPA binds to the genomic progesterone receptor (PGR) with high affinity²⁻⁵, leading to the theoretical clinical concern that using UPA in close succession with hormonal contraception may adversely impact the effectiveness of either or both methods. A pharmaceutical-sponsored trial under review for publication studied the impact of UPA on the ability of combined oral contraception (COC) to suppress ovulation. Moreover, that study was not designed to determine COC's impact on UPA (*personal communication, [name], 3/2015*). This knowledge gap places women at further risk for unplanned pregnancy. A woman choosing to take UPA and wanting to initiate a hormonal method can either (1) delay initiation of a hormonal contraception for 14 days or until her next menstrual cycle^{8,9} and continue to be at risk for pregnancy using a less effective barrier method or (2) immediately initiate the method and possibly decrease the effectiveness of UPA. Discussions during the CDC Working Group for US Selected Practice Guidelines for Contraceptive Use (Atlanta, GA 10/2011) as well as the recent WHO Medical Eligibility Steering committee meeting (2014) noted that this issue should be a priority in light of increasing UPA use.

Our proposal has been designed to address this gap in knowledge and will focus on the impact of COCs on UPA's main mechanism of action. **Our hypothesis is that starting COCs shortly after UPA use adversely impacts UPA's ability to delay ovulation.** Our primary aim is to define whether starting COCs 2 days following the administration of the anti-progestin, UPA, interferes with its efficacy as an EC. The goal of this aim is to obtain evidence to support or refute the current recommendation to have women using UPA for EC to wait to delay initiation of their hormonal method. Our proposed studies focus on the interaction of COCs and UPA as COCs are one of the most commonly used hormonal methods.

Glasier et al¹¹ demonstrates that there may be differences in the effectiveness of UPA EC in women of varying BMIs. Drug therapeutics or how well a drug works is based on several key pharmacokinetic parameters – specifically for EC, maximum concentration and time to maximum concentration are considered critical. We would like to perform a substudy within this proposal to obtain pilot data to determine if there is a difference in pharmacokinetic parameters between obese and normal BMI women taking UPA-EC.

Methods:

Study design: Prospective cohort study. Women will act as their own controls.

Study Population: Women (total=34) of reproductive-age with a BMI of 18.5-28 will be recruited from the Portland area. To account for screen fails and dropouts, we plan to enroll up to 60. Individuals will be recruited through several different venues using IRB approved materials including flyers, internet recruiting, and the CWH website. Individuals meeting inclusion and exclusion criteria for the

study will be enrolled following completion of informed written consent. The only contraindication for use of UPA-based EC is known current pregnancy but participants will also be exposed to COCs. Study inclusion and exclusion criteria include:

Major inclusion criteria include:

- Generally healthy women aged 18 to 35 with regular menses (every 21-35 days).
- BMI of 18.5-28
 - Additional substudy group of 5 women will have BMI >28
- Proven ovulation with a screening serum progesterone of ≥ 3 ng/mL
- Willing to use condoms (if sexually active with a male partner), willing to not have sex with men during the study, or have had a tubal ligation (or have a partner who has had a vasectomy) or have a copper IUD.

Major exclusion criteria include:

- Known intolerance or allergy to any of the study medication
- Known metabolic disorders including polycystic ovarian syndrome or uncontrolled thyroid disorder
- Overweight or obese BMI (except for additional substudy group of 5 women)
- Any CDC Medical eligibility criteria category 3 or 4 for COC use¹².
- Pregnancy, breastfeeding, or seeking pregnancy; recent (8 week) use of hormonal contraception
- Current use of drugs that interfere with metabolism of sex steroids
- Smokers.

General methods: Subjects will undergo a referent cycle (Cycle 1, UPA only), followed by a washout cycle (Cycle 2) and finally UPA with COCs dosed 2 days later (Cycle 3, treatment cycle) (see **Table 1**). Due to the extensive number of visits, blood draws, and exams, the patients will be compensated for their time. Subjects will either receive compensation through the Greenphire debit card system or as a check. During the referent and treatment cycles (Cycle 1 and 3, respectively), subjects will undergo every other day visits starting on cycle day 6 followed by daily visits for up to 7 days once a dominant follicle measuring 15mm or greater in one diameter is visualized. At each visit, subjects will undergo blood sampling via a single venipuncture for P and LH levels and transvaginal ultrasonography (TUS). Study medication will be dosed on the day a 15 mm follicle is visualized. Women will be given a single dose of 30 mg UPA orally in Cycle 1 or a single dose of 30 mg UPA orally followed 2 days later by a COC (0.150 mg levonorgestrel/30 μ g of ethinyl estradiol) in Cycle 3. Prior to ingesting study medication, women will undergo urine pregnancy testing. Women can choose to continue the COC for the entire 21 days or they can discontinue after 7 days. Women will have a washout cycle between the referent and treatment cycles where they will remain in contact with study staff for scheduling and retention purposes but will not have any scheduled study visits. Study end will be at the onset of menses (defined as two consecutive days of spotting/bleeding).

Table 1. Study flow (n = 34)

	+ing	Cycle 1 Referent cycle UPA only	Cycle 2 Washout	Cycle 3 UPA+COC 2 days later
Study Procedures	Luteal phase ovulation testing	-Starting day 6 until 15 mm follicle: every other day P, LH, & TUS -15 mm follicle: study medication dosed and daily P, LH, & TUS for up to 7 days		-Starting day 6 until 15 mm follicle: every other day P, LH, & TUS -15 mm follicle: study medication dosed and daily P, LH, & TUS for up to 7 days -COCs dosed 2 days after study medication

Data Analysis & Sample Size:

The primary outcome will be the difference in the proportion of women with a delay in follicular rupture up to 5 days (yes/no) between their referent and treatment cycles¹³. Follicle rupture will be defined as the disappearance or >50% reduction of size of the leading follicle. Confirmation of ovulation will be supported by LH and P levels. Demographics will be reported and descriptive statistics will be utilized to report LH and P levels [mean (standard deviation)], follicular diameter [median (range)], and cycle day [median (range)] on the day of UPA ingestion during the referent and treatment cycles. Additionally, inhibition of follicular rupture will be plotted by LH status (no surge, start of LH surge, or after LH peak; defined in Brache et al.¹³) for each cycle as well as mean LH and P levels over time and the time of treatment to follicular rupture.

A sample size of 34 will achieve 82% power to detect a 15% difference in the proportion of cycles that demonstrate at least a 5-day delay in follicular rupture (yes/no) using a two-sided exact binomial test with a 5% significant level. We plan to recruit up to 60 women to account for drop out. We based this assumption on the overall effect of UPA which causes persistence of the dominant follicle for at least 5-days in 58% of cycles¹³. If COCs adversely impact UPA by 15% then UPA's efficacy would be similar to that of a levonorgestrel-EC which would be clinically significant.

Substudy: UPA Pharmacokinetics

Our control group (normal BMI) will be recruited from women enrolling in the main study. Up to 5 women enrolled in the main study may choose to participate in this substudy. They may choose to participate in this substudy either during Cycle 1 or Cycle 3, whichever cycle is most convenient for them. The substudy will be performed over 1 visit but this visit will take approximately 3 hours to complete. During this visit, women will undergo serial blood sampling from a "single stick" venipuncture or from an indwelling intravenous catheter – per the subject's choice. One tube (10mL) of venous blood will be collected at the following time intervals in conjunction with UPA ingestion (0, 0.5, 1, 1.5, 2, 2.5 hours). UPA will be ingested under fasting conditions and directly observed intake will occur. Women volunteering for this substudy will be compensated for this additional time. An additional 5 obese women will be recruited only to participate in this substudy as obesity is an exclusion criteria for the main study. This group must meet the main study's eligibility criteria except for BMI and confirmed ovulatory status by P value. Serial blood sampling will be timed to occur during the follicular phase of the obese participant's menstrual cycle.

Human subjects protection:

Human Subjects Involvement and Characteristics. Reproductive-aged (18-35 year old), ovulatory, healthy women with no contraindications to the study medications and not at risk for or seeking pregnancy will constitute the target population for this study.

Setting. All enrollment and clinical evaluations will be performed at OHSU in Portland, Oregon. Serum samples will be prepared at OHSU and analyzed at the ONPRC Endocrine Core Laboratory under the direction of [name].

Sources of Materials. The sources of research material for the clinical portion of this proposal will be new specimens (blood) and ovarian ultrasound data obtained purely for this research protocol. The study investigators and/or research assistants/nurses will perform all study procedures.

Potential Risks. In regard to the UPA-based emergency contraceptive used in this study, the only contraindication to this medication is current pregnancy (CDC 2013) and this is an exclusion criterion for study participation. The use of EC can affect the timing and duration of a woman's next menstrual period and very rarely can cause nausea and/or headache. This information will be reviewed with participants and if necessary, an anti-emetic can be provided. For the COC utilized in the study, we will use a COC that is commercially available and screen women according to the CDC Medical eligibility for contraceptive use guidelines. We plan to use these medications in accordance with FDA-labeling.

Women may feel some pain when their blood is drawn through venipuncture or the use of an indwelling venous catheter but there is minimal risk involved. There is a small chance the needle will cause bleeding, a bruise, or an infection.

There are no known harmful effects of a transvaginal ultrasound. Women may experience slight vaginal discomfort.

Risk of pregnancy is always present in women who are sexually active. Women who are not at risk for pregnancy due to the use of permanent contraception (male or female), use of a copper IUD, or have a female partner will be eligible for the study. Those women at potential risk of pregnancy will be asked to abstain or to use condoms for the duration of the study.

Recruitment and Informed Consent. Attempts to enroll a diverse study population will be made through placement of IRB approved recruitment material in the community, community outreach such as receiving an emailed newsletter they have opted to receive, and through the availability of foreign language interpreters and research staff. Women may also learn of the study through their routine visits in clinics or by working at OHSU.

Women will be screened for eligibility and if they meet the basic criteria and agree to participate, they will undergo informed written consent. The protocols and consent will be reviewed and approved by the OHSU IRB prior to initiation of the study. Information we collect and create in order to conduct and oversee this research study will be stored in the Women's Health Research Unit repository (IRB# 6748) for possible future research.

Protection Against Risk. Confidentiality of personal health information will be maintained according to HIPAA requirements for research. All subjects will receive a study number to which all subsequent data will refer. Personal identifiers will not be on questionnaires, data, abstract sheets, or in the main

database. All data will be kept in locked files or a password protected computer in the Principal Investigator's (PI) office. We will do our best to keep information confidential by keeping it coded and on password-protected computer.

Potential Benefits of the Proposed Research to the Subjects and Others. There are no direct benefits to study participants.

Importance of Knowledge to be Gained. It is anticipated that the results from this study will determine whether close administration of a COC with UPA will inhibit the ability of UPA to function effectively as an EC. Since UPA works via its ability to serve as a PGR antagonist, the immediate administration of PGR agonists present in COCs will possibly increase the failure rate of UPA due to competing actions on PGR signaling. UPA effects include preventing or delaying the midcycle surge of LH that is critical for ovulation¹¹ and the expression of progesterone (P) regulated genes in the ovulatory follicle necessary for its rupture². Thus, it is necessary to establish whether the PGR agonists present in COCs will negate the ability of UPA to prevent the cellular processes crucial for ovulation and consequently fertilization. This information will be critical for determining when to initiate COCs in women seeking this form of birth control. In addition, our research team is one of only a very few studying molecular and associated clinical aspects of novel and established contraceptives

We anticipate that the study results will provide evidence for direct clinical guidance regarding co-administration of COCs and UPA. We plan to disseminate the data through publication and presentations as well as highlighting the results to relevant governmental entities (e.g., CDC) and interested parties (e.g., HRA Pharma).

References

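### The stated 82% power for a 15-point difference with 34 women does not follow from the protocol's own 58% rate; the two-sided exact binomial test it names gives at most about 41%.

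*Combined protocol and SAP*

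**What the plan says.** The Data Analysis & Sample Size section gives the only sample-size justification in the protocol: "A sample size of 34 will achieve 82% power to detect a 15% difference in the proportion of cycles", where the outcome is a delay in follicular rupture of at least 5 days (yes/no). The test is described as "using a two-sided exact binomial test with a 5% significant level". The assumption is said to rest on ulipristal causing "persistence of the dominant follicle for at least 5-days in 58% of cycles". A 15% adverse effect is described as clinically important because it would bring ulipristal close to levonorgestrel emergency contraception.

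The design is within-woman. Under Study design the protocol says "Women will act as their own controls", and the primary outcome compares women "between their referent and treatment cycles". No discordant-pair proportion or within-woman correlation is given, and the text does not say whether the binomial test is one-sample or on the pairs.

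On the larger enrolment figure, the sample-size paragraph says "We plan to recruit up to 60 women to account for drop out", and Study Population says "To account for screen fails and dropouts, we plan to enroll up to 60". Table 1 is also headed with n = 34.

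**The concern.** A 15-point difference in a proportion near one half is small for 34 women, paired or not, so 82% looks too high on its face.

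The Background gives the trial's goal as to "obtain evidence to support or refute the current recommendation" to delay hormonal contraception after ulipristal. A reader who trusts the 82% would take a non-significant result as fair evidence against a 15-point loss. If real power is 40% or less, a non-significant result is the more likely outcome even when that loss is present.

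**Working it through.** **Inputs from the protocol:** n = 34; reference rate 58%; difference 15%, read as percentage points (58% to 43% is the direction of concern, 58% to 73% the reverse); two-sided exact binomial test at 5%; stated power 82%. Reverse discordance is not given, so the values used below are assumptions.

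**1. One-sample exact binomial test against 58%.** Let X be the number of women, out of 34, with a delay. With at most 2.5% in each tail under Bin(34, 0.58):

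- Reject if X ≤ 13 (probability 0.0159) or X ≥ 26 (0.0199). Actual size is 0.0159 + 0.0199 = 0.0358.
- Power at 43% is P(X ≤ 13) + P(X ≥ 26) under Bin(34, 0.43) = 0.3519 + 0.0001 = **35.2%**.
- Power at 73% is **40.8%**.
- Reading 15% as relative (58% to 49.3%) gives 13.3%.

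**2. Exact McNemar test, the exact binomial test for paired data.** Let p10 be the probability of a delay in Cycle 1 but not Cycle 3, and p01 the reverse, with p10 − p01 = 0.15. The p-value is twice the smaller Bin(m, 0.5) tail, where m is the number of discordant pairs.

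The best case can be checked by hand:

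- 5 of 5 in one direction gives p = 2 × 0.5⁵ = 0.0625, not significant.
- 6 of 6 gives p = 2 × 0.5⁶ = 0.031, significant. At least 6 discordant pairs are needed.
- With p01 = 0, the expected number of discordant pairs is 34 × 0.15 = 5.1.
- P(Bin(34, 0.15) ≤ 5) = 0.597, so power = 1 − 0.597 = **40.3%**.

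This is the maximum over p01 from 0 to 0.42. Under independence p10 = 0.58 × 0.57 = 0.3306 and p01 = 0.42 × 0.43 = 0.1806.

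| Assumed reverse discordance p01 | Power, 34 pairs | Loss giving about 82% power, 34 pairs | Completed pairs for 82% at 15 points | Power at 15 points, 60 pairs |
|---|---|---|---|---|
| 0 | 40.3% | 23 points (82.7%) | 53 | 90.3% |
| 5% | 28.9% | 32 points (82.7%) | 97 | 58.1% |
| Independent cycles (18.06% at a 15-point loss) | 16.8% | 36–37 points (81.0%, 83.6%) | 197 | 29.8% |

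**3. Attempts to recover 82% at n = 34 with other tests.** One-sided one-sample exact: 48.7% (to 43%) and 56.1% (to 73%). Normal-approximation one-sample: 42.6% two-sided, 55.0% one-sided. One-sided or mid-p McNemar with no reverse discordance: 59.2%. Asymptotic McNemar in the same case: 62.7% two-sided, 74.7% one-sided. Two independent groups of 34: 23.2%. None reaches 82%.

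**4. Rates that would give 82%.** A one-sample two-sided exact test at n = 34 has 82.0% power for a null of 4.5% against 19.5%, or the mirror image of 95.5% against 80.5%. The protocol mentions no such rates.

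**The case against.** Four points can be made for the plan.

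- **Other exact tests do better.** An unconditional exact paired test ordered on the z statistic rejects at 5 of 5 discordant pairs with n = 34 (maximum size 0.041). Its power is 59.2% with no reverse discordance, 39.4% at 5% and 20.2% under independence. So the 41% ceiling belongs to the exact binomial test, and the 60% miss rate depends on using it. That stands. But the exact binomial test is the one the protocol names, and 59.2% is still far from 82%.
- **The 82% may come from unreported inputs.** This is possible, since step 4 shows rates that yield it. The source is unknown, and the claim made here is only that 82% does not follow from the stated inputs. The protocol names 58% as its basis.
- **Up to 60 women may be enrolled.** If all 60 completed, power would be 90.3% with no reverse discordance and 81.5% with 1%, but 58.1% with 5%. The power claim is made for 34, and the protocol assigns the extra enrolment to screen failures and dropout.
- **The plan has no rule that a non-significant result means no interaction.** True, so the harm depends on how the result is read. The stated goal of supporting or refuting a recommendation invites that reading.

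**Conclusion.** The concern holds. From the protocol's 58% rate, 34 women and a two-sided exact binomial test at 5%, power for a 15-point difference is 35.2% to 40.8% as a one-sample test and at most 40.3% as a paired test, against the 82% stated. The paired maximum requires no assumed discordance, because it is the best case; the lower paired figures (28.9%, 16.8%) rest on assumed reverse discordance. Reading the 15% as percentage points favours the plan, since the relative reading gives 13.3%. This must be corrected, because it is the sole justification of the sample size for the primary outcome and overstates power at least twofold (82 / 40.8 = 2.0).

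**What to change.** In Data Analysis & Sample Size, name the two-sided exact McNemar test on the within-woman pairs (Cycle 1 versus Cycle 3) as the primary test, delete the 82% claim, and replace it with text such as:

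> 34 completed pairs give at most about 40% power for a 15-point loss from 58% (two-sided exact McNemar, 5%, assuming no reverse discordance), and about 17% if a woman's two cycles are assumed independent. About 82% power is reached only for a loss of about 23 points (assuming no reverse discordance) to about 36–37 points (assuming independence). The discordance values are assumptions. Enrolment of up to 60 allows for screen fails and dropout.

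If the investigators hold a calculation that gave 82%, they should report its null and alternative rates and its test, so that it can be checked.

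The cost is protocol wording only. The correction itself requires no extra enrolment; the price is a less favourable power statement. It does not make the trial adequately powered for 15 points, which on the same assumptions would take 53 to 197 completed pairs.
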